6.2.3.7. Joint Counts (TJC68/SJC66)

The joint counts (TJC68 and SJC66) will be evaluated on the visits specified in the Schedule of Assessments (See Section 2.5). Each of 68 joints will be evaluated for tenderness (tender joint count, TJC68), and each of 66 joints will be evaluated for swelling (swollen joint count, SJC66).

6.2.3.7.1 Derivation Rules

The assessment for swelling is the total number of joints with a present swelling and ranges from 0 to 66 for SJC66. The assessment for tenderness is the total number of joints with a present tenderness and 0 to 68 for TJC68.

In case not all 68 (66) joints are scored in the investigator "66/68 Swollen and Tender Joint Count" electronic diary (eCOA), then it is assumed that the joints that are not scored are not tender (swollen). In case there are permanently or temporarily unassessable joints (assessment 'Not applicable'), then no action is taken (so actually these are counted as not tender and not swollen).

If the overall 68 (66) joints count assessment is not performed at all ("Was the assessment performed?" ticked 'No' in the electronic case report form (eCRF), TJC68 and SJC66 will be set to missing.

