ICH	International Council for Harmonisation of Technical Requirements for Pharmaceuticals for Human Use
IEC	Independent Ethics Committee
IgG	immunoglobulin G
IL	interleukin
IP	investigational product
INR	international normalized ratio
IRB	Institutional Review Board
IXRS	interactive voice/web response system
JAK	Janus kinase
LDL	low-density lipoprotein
LFT	liver function test
LPS	lipopolysaccharide
LRV	lower reference value
MMRM	mixed models for repeated measures
mRNA	messenger ribonucleic acid
MTX	methotrexate

NOAEL	no-observed-adverse-effect level
NSAID	non-steroidal anti-inflammatory drug
P1NP	serum N terminal propeptide type I collagen
PBMC	peripheral blood mononuclear cells
█	███████████
PK	pharmacokinetic
pop-PK	population pharmacokinetics
q.d.	once daily
QTcF	QT interval corrected for the heart rate using Fridericia's formula
QTv	QT interval corrected by heart rate using the van de Water formula
RA	rheumatoid arthritis
SAE	serious adverse event
SAP	statistical analysis plan
SBP	systolic blood pressure
SD	standard deviation
█	███████████
SIK	salt-inducible kinase
SJC66	swollen joint count evaluated in 66 joints
SOC	System Organ Class
SUSAR	suspected unexpected serious adverse reaction
$t_{1/2}$	elimination half-life
TB	tuberculosis
TEAE	treatment-emergent adverse event
TJC68	tender joint count evaluated in 68 joints

TNF	tumor necrosis factor
TNFi	tumor necrosis factor inhibitor
TV	target value
ULN	upper limit of normal
VAS	visual analog scale
Vss	volume of distribution at steady state
WOCBP	women of childbearing potential

Definition of Terms

BMI body mass index

Weight (kg) / (height [m])²

QTcF QT interval corrected for heart rate using Fridericia's formula:

$$QTcF = QT/RR^{1/3}$$

RR = the interval from the onset of one QRS complex to the onset of the next QRS complex

DAS28 (CRP) disease activity score based on 28 joints

DAS28 (CRP) = 0.56 x $\sqrt{\text{TJC28}}$ + 0.28 x $\sqrt{\text{SJC28}}$ + 0.36 x $\text{Ln}[1+\text{CRP}(\text{in mg/L})]$ + 0.014 x patient's disease activity visual analog scale (VAS, in mm) + 0.96 (Mack, Hsia, & Aletaha, 2017)

TJC28 and SJC28 are the 28 joint counts for tenderness and swelling.

Ln = natural logarithm.

HOMA-IR Homeostatic model assessment of insulin resistance

HOMA-IR = (fasting insulin [mU/mL] x fasting glucose [mg/dL])/405

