6.2.2. Primary Efficacy Parameter

The primary endpoint for this study is the change from baseline in DAS28 (CRP) at Week 6. The DAS28 (CRP) is a derived measurement with differential weighting given to each component such as TJC28, SJC28, patient's global assessment of disease activity (0–100-mm VAS), and serum CRP level. A DAS28-CRP below the value of 2.6 is interpreted as Remission.

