6.2.2.1. Derivation Rules

The DAS assessment is a derived measurement with differential weighting given to each component. The DAS28 (CRP) will be calculated at each assessment time point.

The components of the DAS28 arthritis assessment include:

- Tender Joint Count 28 (TJC28) ranges from 0-28
- Swollen Joint Count 28 (SJC28) ranges from 0-28
- High sensitivity C-reactive protein (hsCRP) (in mg/L)
- Patient's disease activity VAS (in mm) (ranges from 0 = best to 100 = worst)

The DAS28 (CRP) score will be calculated using the below formula:

$$\text{DAS28 (CRP)} = 0.56 \times \sqrt{\text{TJC28}} + 0.28 \times \sqrt{\text{SJC28}} + 0.36 \times \text{Ln}[1+\text{CRP}(\text{in mg/L})] + 0.014 \times \text{patient's disease activity VAS} (\text{in mm}) + 0.96 \text{ (Mack, Hsia, \& Aletaha, 2017)}$$

where Ln is the natural logarithm

A lower score is considered as better disease activity. If one of the component is missing at a specific analysis visit, DAS28 (CRP) will not be calculated for that assessment and will be set to missing.

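### SAP 6.2.3.7.1 counts unscored and unassessable joints as healthy; a partly completed joint form understates TJC68/SJC66 and, by inference, the primary DAS28 (CRP) at that visit

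*SAP*

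**What the plan says.** SAP 6.2.3.7.1 (Derivation Rules for TJC68/SJC66) covers three situations.

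- **Some joints not scored:** "then it is assumed that the joints that are not scored are not tender (swollen", the bracketed word extending the rule to the swollen count.
- **Joints permanently or temporarily unassessable:** no action is taken, "so actually these are counted as not tender and not swollen".
- **No joint assessment:** "If the overall 68 (66) joints count assessment is not performed at all", both counts are set to missing. This is the only route to a missing count.

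The primary endpoint is defined in SAP 6.2.2: "The primary endpoint for this study is the change from baseline in DAS28 (CRP) at Week 6". Its joint components are TJC28 and SJC28, each running from 0 to 28 (SAP 6.2.2.1). On missing data that section says: "If one of the component is missing at a specific analysis visit, DAS28 (CRP) will not be calculated for that assessment". It does not say what happens when a 28-joint count comes from a partly scored form, and it does not refer to 6.2.3.7.1.

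Protocol 8.4.1 and SAP 6.2.3.7 name only one joint assessment, 68 joints for tenderness and 66 for swelling.

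**The concern.** A joint nobody examined is entered as a healthy joint. This departs from the SAP's own approach to missing results. Section 4.3.6.2 makes no imputation the default, and where it does impute (some binary endpoints) a missing value becomes a non-response. Here the missing piece is filled with the favourable value.

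A partial form also still yields a number. If the rule carries over to the 28-joint counts, the missing-component safeguard in 6.2.2.1 does not act, and DAS28 (CRP) is calculated from an understated count. The same score then feeds the remission cut at 2.6 and the activity categories in 6.2.3.1.1.

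The rule anticipates temporarily unassessable joints, whose status can differ between visits. In that case part of a subject's change from baseline comes from the form rather than the disease.

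**Working it through.** **Inputs from the documents**
- Joint part of DAS28 (SAP 6.2.2.1): J(T, S) = 0.56√T + 0.28√S, with T = TJC28 and S = SJC28. Both weights are positive, and "A lower score is considered as better disease activity".
- SD 1.3 in both arms, 15 + 10 subjects (SAP 2.6); TV -1.6 and LRV -0.6 with the P10/P80 rules (SAP 6.2.2.3).

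**Assumptions (not in the documents):** the T and S values below and the number of joints skipped.

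**1. The plan's own scale.** The plan gives no figure for partial forms; its nearest figures are the operating characteristics in SAP 2.6. SE = 1.3 × √(1/15 + 1/10) = 0.531. A signal needs estimate + 0.842 SE < -0.6 and estimate - 1.282 SE < -1.6. No signal means estimate - 1.282 SE ≥ -1.6.

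| True difference | Signal / no conclusion / no signal, recomputed | SAP 2.6 |
|---|---|---|
| -1.6 | 0.851 / 0.049 / 0.100 | 0.852 / 0.043 / 0.105 |
| -0.6 | 0.200 / 0.073 / 0.727 | 0.192 / 0.091 / 0.717 |

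All six agree within 2 percentage points, so 0.53 is a fair yardstick.

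**2. One subject, one visit.** Fall in DAS28 when every unscored joint is among the 28 and truly both tender and swollen:

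| True T/S | 2 lost | 4 lost | half of active joints lost |
|---|---|---|---|
| 16/12 | 0.23 | 0.48 | 0.94 |
| 12/10 | 0.26 | 0.56 | 0.83 |
| 8/6 | 0.34 | 0.75 | 0.67 |

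For 12/10 with 4 lost: J(12, 10) = 1.940 + 0.885 = 2.825 and J(8, 6) = 1.584 + 0.686 = 2.270, a fall of 0.56.

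If instead 4 of the 28 joints are skipped at random, the expected loss is 12 × 4/28 = 1.71 tender and 10 × 4/28 = 1.43 swollen. J(10.29, 8.57) = 2.616, a fall of 0.21. If the skipped joints were inactive, the fall is zero.

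**3. Direction in the change from baseline.** Assume baseline 16/12 and true Week 6 12/9, so the true joint-part change is -0.43. With 4 active joints unscored:
- at Week 6 only: J(8, 5) - J(16, 12) = -1.00, too much improvement;
- at baseline only: J(12, 9) - J(12, 8) = +0.05, improvement hidden;
- at both visits, same persistently active joints: J(8, 5) - J(12, 8) = -0.52, close to the truth.

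**4. Arm level.** Two subjects with a fall of 0.556: 2 × 0.556/15 = 0.07 in the GLPG3970 arm, or 2 × 0.556/10 = 0.11 in the placebo arm. With random skipping: 2 × 0.21/15 = 0.03, or 2 × 0.21/10 = 0.04. The yardstick is 0.53.

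**5. Effect on the decision rule if the arms are unbalanced.** Three of 15 GLPG3970 subjects with a spurious fall of 0.5 give a net -0.10 (3 × 0.5/15). The chance of a signal at a true -0.6 then rises from 0.200 to 0.257. Two of 10 placebo subjects with the same fall give a net +0.10. The chance of a signal then drops to 0.151 at a true -0.6, and from 0.851 to 0.803 at a true -1.6.

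**6. Proration.** Same subject as in step 3, with a quarter of the joints unscored at Week 6 and activity spread evenly, so 9 tender and 6.75 swollen are seen on 21 joints. The current rule gives J(9, 6.75) - J(16, 12) = -0.80. Scaling by 28/21 restores 12/9 and gives -0.43, the true change.

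**The case against.** The strongest objection is that the rule sits under secondary parameters and names only TJC68 and SJC66. Section 6.2.2.1 does not cite it. SAP Section 1 places technical derivation details in a separate document, parts of 6.2.3 are redacted, and the joint-count appendix is not in the available text, so a 28-joint rule may exist elsewhere. This stands as a limit: the carry-over to the primary endpoint is the natural reading, but it is an inference.

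A reader might infer that the rule biases the primary endpoint one way, toward improvement or in favour of GLPG3970. The documents do not support that. The endpoint is a change, and a partial baseline form works against improvement. Permanently unassessable joints are counted alike at both visits. Allocation is double-blind, and equal rates of partial forms cancel between arms. Nothing in the plan suggests a systematic imbalance.

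A reader might also set the 0.56 fall beside the LRV of 0.6. That compares one subject with a difference between arm means, and it takes every skipped joint as active. The like-for-like figures are those in step 4.

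Nor do the documents show that pandemic home visits would produce partial forms. Protocol Sections 5.5 and 8 restrict them to trained staff, 8.4.1 requires a designated joint assessor and a back-up, and a visit without any joint assessment is set to missing.

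Finally, proration has its own assumption, that unassessed joints are as active as assessed ones. That is fair, and it is why the fix keeps the current rule as a sensitivity analysis.

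**Conclusion.** The point holds as a defect in a stated derivation rule. For TJC68 and SJC66 it is explicit: an incomplete form gives a count that is too low whenever an unscored joint was active. Those counts go into the MMRM on percent change (SAP 6.2.3.7.2). For DAS28 (CRP) it holds by inference; if the inference is wrong, the visible text of 6.2.2.1 still has no partial-form rule for the primary endpoint.

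For one subject the error ranges from nothing to about half a DAS28 point or more, under assumed joint counts. For an arm mean it is about 0.03 to 0.11 with two affected subjects, small against a standard error of 0.53. It enters the treatment difference only if partial forms differ between arms, which chance alone can produce with 15 and 10 subjects, and it can then act in either direction. The documents give no rate of partial forms, so the trial-level effect cannot be stated. The change is worth making because the rule yields a wrong count and a better one is cheap.

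**What to change.** In SAP 6.2.3.7.1, and by explicit statement in 6.2.2.1:

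- Prorate each count over the joints assessed: active joints / joints assessed × 28, 66 or 68, when at least a pre-stated share (for example half) was assessed.
- Below that share, set the count to missing, and DAS28 (CRP) with it.
- Apply the same rule at baseline and all later visits.
- Leave joints that are unassessable throughout the study out of the assessed set at every visit.
- Report the current rule as a sensitivity analysis, and tabulate the number of partial forms by arm and visit.

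The cost is about a paragraph in the SAP and a small programming change. SAP 6.2.3.7.2 already lists individual joints, so the data exist. Two downsides remain. A few visits may become missing, which the MMRM accommodates through the likelihood (SAP 4.3.6.2). Proration also assumes that unassessed joints resemble assessed ones, and the minimum share is a judgement to be fixed before unblinding.

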6.2.3.7.2 Analysis Methods

Observed, change from baseline and % change from baseline values over time will be summarized using descriptive statistics by treatment group and visit for the TJC68 and SJC66 separately.

An MMRM model will be used on the percent change from baseline to compare the treatment groups (GLP3970 vs Placebo). For the presentation of results refer [section 6.2.2.2](#). Listing will include all individual TJC68 and SJC66 joints along with total score.

6.2.3.8.

The figure consists of a 10x10 grid of black bars on a white background. The bars are of various lengths and are positioned in a staggered, non-overlapping manner. Some bars are longer than others, and they are placed in a way that creates a sense of depth or a stepped pattern. The bars are black and have a uniform thickness.

6.2.3.9.1 Derivation Rules

Not applicable.

6.2.3.9.2

A series of 15 horizontal black bars of varying lengths, starting with a short bar and increasing to a very long bar, then decreasing again. The bars are arranged vertically, with the longest bar at the top and the shortest at the bottom. The lengths of the bars are approximately: 10, 15, 20, 25, 30, 35, 40, 45, 50, 55, 60, 65, 70, 75, 80, 85, 90.

6.3. Safety Analyses

Safety analyses will be performed on the Safety Analysis Set.

Safety tables will be presented by treatment group and overall.

Safety parameters will be analyzed descriptively (see Section 4.4.2 and Section 4.4.3). No formal testing will be performed to compare the treatment groups.

6.3.1. Adverse Events

All AEs and changes in attributes (worsening and improvement) of AEs are reported in the database. An identification number serves to link the records considered by the investigator as describing the evolution of one and the same event.

6.3.1.1. Definition of Treatment-Emergent Adverse Events

The analysis of AEs will be based on treatment-emergent events (TEAE). TEAEs are defined as

- Any AE with an onset date on or after the IP start date and no later than 14 days after last dose of IP, or any worsening of any AE on or after the IP start date.
- Improvement or no change of any ongoing AEs on or after the IP start date are not considered treatment-emergent. If an AE is ongoing at the time of first IP intake, if there is no change or an improvement in its toxicity grade or its seriousness status (reported in the 'Change in Adverse event details Entry' CRF page), this AE will not be considered as treatment-emergent.

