8.11. Schedule of Activities

For detailed instructions on the clinical study procedures, please see referred sections and Section 8.1, “[Timing of Assessments](#)”.

EVENT	SCREENING PERIOD	TREATMENT PERIOD ^{1,2}						FOLLOW-UP PERIOD ²
		1	2	3	4	5	ED ³	
Study visit	S	1						FU Visit
Study Weeks		Baseline	1	2	4	6		
Study Day (D) ± Days	-21 to -1	1	8 ± 2	15 ± 2	29 ± 2	43 ± 2	Early treatment discontinuation	57 ± 3
On site visit	✓	✓		✓	✓	✓	✓	✓
Telephone call			✓					
Informed consent	✓							
Inclusion/exclusion criteria	✓	✓						
Demographics	✓							
Medical history	✓							
FSH test (postmenopausal women)	✓							

¹ On dosing days, all assessments are to be performed within 3 hours pre-dose, unless otherwise specified.

² Subjects must come for the study visits 1, 3 and 5 in the morning in a fasting state (no food intake for at least 8 hours). For Visit 1 (predose measurements) and for 2 post dose visits (Visit 3, 4 or 5) all attempts should be made to plan the visit within 2 days following MTX intake.

³ Subjects who discontinue treatment early will be requested to return for an early discontinuation (ED) visit to complete all Visit 5 assessments and to return for a follow-up (FU) visit 14 ± 3 days after last IP administration.

EVENT	SCREENING PERIOD	TREATMENT PERIOD ^{1,2}						FOLLOW-UP PERIOD ²
		1	2	3	4	5	ED ³	
Study visit	S	1						FU Visit
Study Weeks		Baseline	1	2	4	6		
Study Day (D) ± Days	-21 to -1	1	8 ± 2	15 ± 2	29 ± 2	43 ± 2	Early treatment discontinuation	57 ± 3
Pregnancy test ⁴	✓	✓			✓	✓	✓	
Physical examination	✓	✓				✓	✓	✓
Vital signs	✓	✓		✓	✓	✓	✓	✓
Body weight and height ⁵	✓	✓		✓	✓	✓	✓	✓
12-lead triplicate ECG	✓	✓		✓	✓	✓	✓	✓
Serology	✓							
QuantiFERON-TB Gold test	✓							
SARS-CoV-2 RT-PCR test ⁶	✓	✓	As needed					
SARS-CoV-2 serology test ⁶		✓	As needed					
Randomization		✓						
Clinical safety blood samples	✓	✓ ⁷		✓ ⁷	✓	✓ ⁷	✓	✓

⁴ Serum beta human chorionic gonadotropin at screening, baseline (Visit 1), Visit 4 and Visit 5, or at the ED visit, if applicable (all female subjects).

⁵ Height only to be measured at screening.

⁶ RT-PCR from a nasal swab sample at screening and RT-PCR from a nasal swab sample and serology testing at baseline (Visit 1), and as needed when subject presents signs and symptoms of SARS-CoV-2 infection.

⁷ Fasted glucose, fasted insulin and HOMA-IR only at Visit 1, 3 and 5 and the ED visit, if applicable.

EVENT	SCREENING PERIOD	TREATMENT PERIOD ^{1,2}						FOLLOW-UP PERIOD ²

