9.3.5. Analyses of Safety Data

All safety analyses will be performed using the Safety Analysis Set (Section 9.2.4). All safety data collected on or after the first dose of IP administration up to the last contact after the last dose of IP, unless specified otherwise, will be summarized by treatment group according to the IP

received. Clinical safety will be addressed by assessing AEs, laboratory assessments, physical examinations, vital signs, and 12-lead ECGs.

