2.5. Scheduled of Assessments

The study assessments will be undertaken at time points as specified in the Schedule of Assessments (Table 1). For detailed instructions on the clinical study procedures, please see the relevant CSP sections and CSP Section 8.1, “Timing of Assessments”.

Table 1 Schedule of Assessments

EVENT	SCREENING PERIOD	TREATMENT PERIOD ^{1,2}						FOLLOW-UP PERIOD ²
		1	2	3	4	5	ED ³	
Study visit	S	1						FU Visit
Study Weeks		Baseline	1	2	4	6		
Study Day (D) ± Days	-21 to -1	1	8 ± 2	15 ± 2	29 ± 2	43 ± 2	Early treatment discontinuation	57 ± 3
On site visit	✓	✓		✓	✓	✓	✓	✓
Telephone call			✓					
Informed consent	✓							
Inclusion/exclusion criteria	✓	✓						
Demographics	✓							
Medical history	✓							
FSH test (postmenopausal women)	✓							
Pregnancy test ⁴	✓	✓			✓	✓	✓	
Physical examination	✓	✓				✓	✓	✓

¹ On dosing days, all assessments are to be performed within 3 hours pre-dose, unless otherwise specified.

² Subjects must come for the study visits 1, 3 and 5 in the morning in a fasting state (no food intake for at least 8 hours). For Visit 1 (predose measurements) and for 2 post dose visits (Visit 3, 4 or 5) all attempts should be made to plan the visit within 2 days following MTX intake.

³ Subjects who discontinue treatment early will be requested to return for an early discontinuation (ED) visit to complete all Visit 5 assessments and to return for a follow-up (FU) visit 14 ± 3 days after last IP administration.

⁴ Serum beta human chorionic gonadotropin at screening, baseline (Visit 1), Visit 4 and Visit 5, or at the ED visit, if applicable (all female subjects).

EVENT	SCREENING PERIOD	TREATMENT PERIOD ^{1,2}						FOLLOW-UP PERIOD ²
		1	2	3	4	5	ED ³	
Study visit	S	1						FU Visit
Study Weeks		Baseline	1	2	4	6		
Study Day (D) ± Days	-21 to -1	1	8 ± 2	15 ± 2	29 ± 2	43 ± 2	Early treatment discontinuation	57 ± 3
Vital signs	✓	✓		✓	✓	✓	✓	✓
Body weight and height ⁵	✓	✓		✓	✓	✓	✓	✓
12-lead triplicate ECG	✓	✓		✓	✓	✓	✓	✓
Serology	✓							
QuantiFERON-TB Gold test	✓							
SARS-CoV-2 RT-PCR test ⁶	✓	✓					As needed	
SARS-CoV-2 serology test ⁶		✓					As needed	
Randomization		✓						
Clinical safety blood samples	✓	✓ ⁷		✓ ⁷	✓	✓ ⁷	✓	✓
Clinical safety urine samples ⁸	✓	✓ ⁹		✓	✓	✓ ⁹	✓	✓

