⁵ Height only to be measured at screening.⁶ RT-PCR from a nasal swab sample at screening and RT-PCR from a nasal swab sample and serology testing at baseline (Visit 1), and as needed when subject presents signs and symptoms of SARS-CoV-2 infection.⁷ Fasted glucose, fasted insulin and HOMA-IR only at Visit 1, 3 and 5 and the ED visit, if applicable.⁸ On dosing days, clinical safety urine samples will be taken predose, on the same visit day.⁹ Visit 1 and 5: predose and 2 hours postdose. Calcium and phosphate should only be evaluated at Visits 1 and 5.

EVENT	SCREENING PERIOD	TREATMENT PERIOD ^{1,2}						FOLLOW-UP PERIOD ²
		1	2	3	4	5	ED ³	
Study visit	S	1						FU Visit
Study Weeks		Baseline	1	2	4	6		
Study Day (D) ± Days	-21 to -1	1	8 ± 2	15 ± 2	29 ± 2	43 ± 2	Early treatment discontinuation	57 ± 3
PK blood samples for GLPG3970		✓ ¹⁰		✓ ¹¹	✓ ¹¹	✓ ^{11,12}	✓	
		✓		✓	✓			
		█		█		█		█
		█		█		█		
		█		█		█		
Subject diary evaluation		✓	✓	✓	✓	✓	✓	✓
SJC66/TJC68	✓	✓	✓	✓	✓	✓	✓	
	█	█	█	█	█	█	█	

¹⁰ Visit 1: predose (within 30 minutes prior to dosing), 1 sample within [0.5-1.5 hours postdose] and 1 sample within [2 – 2.5 hours post dose].

¹¹ Visit 3, 4 and 5: predose (within 30 minutes prior to dosing).

¹² Visit 5: 1 sample within [4-6 hours postdose].

¹³

EVENT	SCREENING PERIOD	TREATMENT PERIOD ^{1,2}						FOLLOW-UP PERIOD ²
		1	2	3	4	5	ED ³	
Study visit	S	1						FU Visit
Study Weeks		Baseline	1	2	4	6		
Study Day (D) ± Days	-21 to -1	1	8 ± 2	15 ± 2	29 ± 2	43 ± 2	Early treatment discontinuation	57 ± 3
Dispense IP		✓ ¹⁵		✓ ¹⁵	✓ ¹⁵			
IP administration ¹⁵		Once daily throughout the treatment period						
AE and concomitant medication		throughout the study						

¹⁵ On Visit 1, 3, 4 and 5 administration of IP must occur at site.

[figure not shown]

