3. STUDY ESTIMANDS

Hypothetical and treatment policy estimand for primary efficacy endpoint:

Attribute	Details
Treatments	GLPG3970 (400 mg q.d.) vs. Placebo
Population	
• Population target defined through the inclusion/exclusion criteria (see CSP).• Analysis Set: Full Analysis Set (FAS), defined as all randomized subjects

	who have received at least 1 dose of IP.
Endpoint	Change from baseline in DAS28 (CRP) at Week 6.
Population-level summary	Difference (GLPG3970-Placebo) in least square mean (LSM). For further details see study SAP section 6.2.2.2 .
Intercurrent events and strategies to handle those	
• Early treatment discontinuation (for any reason) is handled using the hypothetical strategy• Other intercurrent events (e.g. major protocol violations, intake of prohibited medication, lack of compliance) are handled using the treatment policy strategy (i.e. they are ignored)

Estimand for the secondary objective (safety)

Attribute	Details
Treatments	GLPG3970 (400 mg qd) vs. Placebo
Population	
• Population target defined through the inclusion/exclusion criteria (see CSP).• Analysis Set: Safety Analysis Set, defined as all subjects who were administered IP at least once.
Endpoint	Presence of TEAE
Population-level summary	Percentage of subjects with TEAEs.
Intercurrent events and strategies to handle these	Intercurrent event: early treatment discontinuation (for any reason): handled using the while-on-treatment strategy. It is expected that no further data collection happens after treatment discontinuation, except of course the normal FU visit. All collected data up to (and including) the last contact FU visit is regarded as possibly

	
influenced by the drug exposure and thus will be used in the analysis.
 
Intercurrent event: major protocol deviations, intake of prohibited/rescue medication, lack of compliance: handled using the treatment policy strategy. All collected data will be used in the analysis.

--	---

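### New AEs stop counting as treatment-emergent 14 days after last dose, but worsening has no end limit, and the estimand text and Treatment period run on to follow-up or last contact

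*SAP*

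**What the plan says.** **TEAE definition (SAP 6.3.1.1; same rule in protocol 9.3.5.2).** A new AE counts if it starts on or after the first dose and "no later than 14 days after last dose of IP". The second limb reads "or any worsening of any AE on or after the IP start date" and carries no end date.

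**Safety estimand (SAP section 3).** Early treatment discontinuation is handled by a while-on-treatment strategy. Under that entry the SAP takes everything gathered through the follow-up visit as potentially "influenced by the drug exposure and thus will be used in the analysis".

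**Follow-up timing (schedule in protocol 8.11 and SAP 2.5).** Early discontinuers are asked to "return for a follow-up (FU) visit 14 ± 3 days after last IP administration". For completers, Visit 5 is Day 43 ± 2 and the follow-up visit is Day 57 ± 3. Visit 5 is a dosing day: "On Visit 1, 3, 4 and 5 administration of IP must occur at site".

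**Collection and allocation.** AEs are collected until the last follow-up visit (protocol 8.5.1 and 11.3.1). The Treatment analysis period ends on the date of last contact (SAP 4.3.2), and AEs are allocated to periods by start date (SAP 6.3.1.3).

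**Reporting.** AE tables show TEAEs only and other AEs are listed (SAP 6.3.1.8). The EudraCT tables are also restricted to TEAEs (SAP 6.3.1.9).

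**The concern.** The plan gives more than one answer to when post-treatment safety follow-up stops counting. A new AE 16 days after last dose is collected and assigned to the Treatment period. In an early discontinuer it is also covered by the estimand statement that the data will be used. It is nevertheless not a TEAE, so it enters no AE table.

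The definition also treats its two limbs differently without giving a reason: on day 16 a worsening counts and a new event does not.

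A related oddity arises at the follow-up visit itself, which includes laboratory tests and an ECG. Treatment-emergent and worst-case laboratory and ECG results use all post-baseline records, including follow-up (SAP 6.3.2.6, 6.3.2.7 and 6.3.3.3). If the visit falls on day 15 or later, an abnormality first seen there can be treatment-emergent in the laboratory or ECG table while a new AE with onset that day is not.

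The number, incidence and severity of TEAEs is a secondary endpoint, and the arms are planned at 15 and 10 subjects, so single events are visible in the percentages.

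**Working it through.** **Inputs.** Visit 5 window, Days 41 to 45, with IP taken on site, so for an on-schedule completer the last dose falls on the Visit 5 day. Follow-up window for completers, Days 54 to 60. Follow-up for early discontinuers, 14 ± 3 days after last dose. TEAE cut-off for new AEs, 14 days after last dose. Planned arms of 15 and 10.

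**1. The plan's own figure.** The follow-up period is stated as 2 weeks. Nominal gap = 57 − 43 = 14 days, which agrees. The cut-off therefore equals nominal follow-up.

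**2. Range within the allowed windows.**

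| Group | Shortest gap | Nominal | Longest gap | Days beyond cut-off, at most |
|---|---|---|---|---|
| Completers | 54 − 45 = 9 | 14 | 60 − 41 = 19 | 19 − 14 = 5 |
| Early discontinuers | 14 − 3 = 11 | 14 | 14 + 3 = 17 | 17 − 14 = 3 |

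No visit deviation is needed to pass day 14. Visit 5 on Day 43 and follow-up on Day 58 give 15 days.

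**3. How often this could arise in completers.** The documents do not give the distribution of visit days. Assume, for illustration only, that every day within each window is equally likely and that the two visits are independent. There are 5 × 7 = 35 combinations. Gaps of 15, 16, 17, 18 and 19 days arise in 5, 4, 3, 2 and 1 of them, so 15/35 = 43% exceed 14 days. Mean uncounted time = (5×1 + 4×2 + 3×3 + 2×4 + 1×5)/35 = 35/35 = 1.0 day per completer, against a mean gap of 14.0 days: 1.0/14.0 = 7% of post-treatment follow-up. The possible range runs from 0 days (all visits by day 14) to 5 days (every completer at the extreme).

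**4. Effect of one subject.** Active: 1/15 = 6.7 points. Placebo: 1/10 = 10 points. This is the shift in a preferred-term incidence when the subject did not already have that term as a TEAE. Overall TEAE incidence moves only if the subject had no other TEAE.

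**5. Passages side by side for a new AE on day 16.**

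| Rule | Treatment of the event |
|---|---|
| AE collection | Recorded, if on or before the follow-up visit |
| Treatment analysis period | Inside |
| Estimand statement (early discontinuer) | To be used in the analysis |
| TEAE definition, new-onset limb | Excluded |
| TEAE definition, worsening limb, same day | A worsening would be included |
| AE tables | Absent; listed only |

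**The case against.** **The estimand sentence is narrower than it looks.** A reader might infer that the SAP promises to use everything to follow-up in all subjects, and hence that a 19-day window conflicts with the estimand. The documents do not support this. The sentence belongs to the early-discontinuation entry, where follow-up reaches 17 days at most, so the direct conflict covers at most 3 days. The 19-day figure concerns completers, for whom the mismatch is with the Treatment analysis period. That period allocates records and does not itself define treatment emergence. The estimand's endpoint is also the presence of a TEAE, which could be read as importing the 14-day rule. That reading is possible, but it leaves the statement that the data will be used without effect for new AEs after day 14.

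**The protocol does not contradict itself or the SAP.** Protocol 9.3.5 speaks of "All safety data collected on or after the first dose of IP administration up to the last contact after the last dose of IP", and a reader might set this against the cut-off. The sentence goes on to allow exceptions specified elsewhere, and protocol 9.3.5.2 specifies one. Protocol and SAP share the 14-day rule, and it matches nominal follow-up, so it may well be deliberate.

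**These are not events that the plan calls drug-related.** The SAP says only that such data may possibly be influenced by exposure.

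**Little is hidden.** All AEs are listed and marked as treatment-emergent or not, all SAEs are listed whether treatment-emergent or not, and safety is descriptive in about 25 subjects. The worsening limb is bounded in practice, because AE collection stops at the last follow-up visit.

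**Visit-date dependence does not argue for a change.** With the present cut-off, the effective window for new AEs in completers is 9 to 14 days. Running to follow-up makes it 9 to 19 days, which is more variable.

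All of this limits the size of the point. It does not explain why new and worsened events have different end points, or reconcile the estimand statement with the tables.

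**Conclusion.** The point holds as an internal inconsistency of small practical size. For early discontinuers, new AEs on days 15–17 fall under data that SAP section 3 says will be used, yet they are excluded from every AE table. For completers, new AEs on days 15–19 are placed in the Treatment period and then excluded in the same way; day 19 requires Visit 5 on Day 41 and follow-up on Day 60. In both groups a worsening on the same days counts.

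Nothing is lost when follow-up takes place by day 14, and listings retain every event. The incidence shifts in the working assume that all planned subjects are treated. The 43% and 1.0-day figures rest on the illustrative visit-day assumption and are not predictions. The documents do not support reading this as a loss of safety information, as a departure of the SAP from the protocol, or as suppression of events judged to be drug-related. Correcting the definition is still worthwhile, because TEAEs are a secondary endpoint and the change is one sentence.

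**What to change.** In SAP 6.3.1.1, define a TEAE as any AE with onset or worsening on or after the IP start date and up to the follow-up visit/last contact, with the same end point for both limbs. This brings the definition into line with the estimand text in SAP section 3 and the Treatment analysis period in SAP 4.3.2. Record it in SAP 6.7, which currently reports no changes, as a change from protocol 9.3.5.2.

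The cost is one sentence plus the SAP 6.7 entry, slightly higher TEAE counts, and a TEAE window that varies with the follow-up visit date. No additional data collection is needed. If the team prefers to keep 14 days, the minimum is to state that limit in the safety estimand and apply it to worsening as well.
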